Fast pH-weighted Molecular Magnetic Resonance Imaging (MRI) using Amine CEST-EPI: The chemical exchange between amine and amide protons in bulk water has been shown to be pH dependent using an imaging method called chemical exchange saturation transfer (CEST) imaging. In a recently set of published studies by [name] and colleagues, pH-weighted imaging was shown to have high spatial correspondence between regions of tumor acidity, elevated choline on MRS, elevated lactate on MRS, and elevated ^{18}F -FDOPA uptake (Figure 4, Harris et al., 2015; Harris et al., 2016). Results also suggested patients with acidic lesions (**Figure 4D**) were more likely to progress earlier after starting radiochemotherapy (**Figure 4F**), while patients with non-acidic lesions (**Figure 4E**) were more likely to respond favorably to therapy. Further, if tumors became less acidic during treatment they were also more likely to have a favorable PFS (Harris et al., 2015). Together, these results suggest characterization of intratumoral pH may be an important biologic feature that should be quantified in GBM patients, particularly for therapies that focus on manipulating the microenvironment, metabolism, or oxygenation.

[figure not shown]

Figure 4: Amine CEST-EPI Imaging

Fast Hypoxia-Weighted MRI using Multi-Echo Spin-and-Gradient Echo (ME-SAGE)-EPI:

Recently, investigators have demonstrated the ability to estimate simultaneous T2 and T2* maps using multi-echo spin-and-gradient echo planar imaging (ME-SAGE)-EPI. Using a combination of T2, T2* and relative cerebral blood volume (rCBV), Magnetic Resonance (MR) estimates of relative oxygen extraction fraction (rOEF) can be acquired (Hirsch et al., 2014; He et al., 2007; Toth et al., 2013). Pilot results suggest these rOEF maps show measurable changes as a result of radiotherapy (**Figure 5**) (Toth et al., 2013). Thus, we will

acquire rOEF maps prior to HIF2a inhibition in order to explore whether patients with relatively hypoxic tumors respond favorably to PT2385. Using a combined multi-echo CEST-SAGE-EPI acquisition we will simultaneously estimate both pH and rOEF in the current study.

[figure not shown]

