9.5.4 Exploratory pH and Hypoxia MRI (All Patients at Select Sites)

The following correlative imaging will be performed at baseline on all patients at sites with advanced imaging capabilities as defined below.

Simultaneous pH- and hypoxia-weighted MRI using multi-echo amine chemical exchange saturation transfer spin-and-gradient echo echo planar imaging (ME-aCEST-SAGE-EPI):

The correlative imaging components of the study are purely exploratory. The purpose is to investigate whether baseline imaging phenotypes derived from pH- and hypoxiaweight imaging predict patients that will respond from inhibition of HIF2a. We hypothesize that patients with acidic or hypoxic tumors will likely express high levels of HIF2a, making these patients particularly amenable to HIF2a inhibitor treatment.

In this study we will perform a single image acquisition to simultaneously quantify pH and hypoxia using a custom multi-echo amine chemical exchange saturation transfer spin-and-gradient echo echo planar imaging (ME-aCEST-SAGE-EPI) technique. We will quantify (1) the magnetization transfer ratio asymmetry at the amine proton off-resonance frequency ($MTR_{asym} @ 3ppm$) as a measure of tumor acidity and (2) R_2' or $rOEF$ estimates ($rOEF = R_2' / (c * rCBV)$) as a measure of tissue hypoxia. These studies will be performed only at baseline, prior to treatment initiation, to explore whether baseline acidity or hypoxia predict patients that will respond to HIF2a inhibition.

Simultaneous pH- and hypoxia-weighted MRI will be performed at baseline only with Siemens 3T MR systems, which are available at 7 of the 11 ABTC sites. Thus, correlative

imaging data will be restricted to those patients enrolled at these sites. Based on prior enrollment data and experience within the ABTC, we anticipate that at least 25 patients (if the study proceeds to full enrollment) or 16 patients (i.e. if early stoppage criteria are met) to be analyzable for this exploratory objective. Of note, this study is not designed to validate these imaging sequences, as all correlative imaging is strictly exploratory and optional. Acidity and hypoxia imaging scans are purely investigational and will NOT be used for efficacy measurements. Efficacy will be determined by radiographic response and PFS using RANO criteria alone.

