The plasma concentration level of each exploratory Pharmacodynamic marker (i.e. EPO, VEGF) will be summarized descriptively (arithmetic mean, standard deviation) at each sample collection time point (pretreatment, 6-hours post-dose, steady state, progression). Their changes from baseline will be presented using standard descriptive statistics and

graphic summaries. Possible association between changes of concentration and clinical outcomes could be explored using statistical modeling techniques.

Hypoxia Imaging

Hypoxia imaging is strictly exploratory. The objective is to describe tumoral hypoxia using advanced MR-based sequences prior to treatment initiation in patients with recurrent GBM. Advanced MRI imaging including CEST and rOEF will be postprocessed as per standard protocols including motion and inhomogeneity correction prior to analysis. Post-processing will be performed by [name] (UCLA, ABTC Imaging Core).

Measurements of Acidic Tumor Volume: Relative pH assessed using MTR_{asym} at 3ppm will be calculated by first performing B_0 homogeneity correction, then calculating the difference in signal intensity between positive and negative offset frequencies divided by the signal intensity with no saturation, $(S_{+3ppm} - S_{-3ppm})/S_0$, for each image voxel. Acidic tumor will be defined as having $MTR_{asym} @ 3ppm > 5\%$ as determined empirically (Harris et al., 2015). Both mean $MTR_{asym} @ 3ppm$ and volume of acidic tumor within contrast enhancing and/or T2 hyperintense tumor regions will be used as exploratory measures of tumor acidity.

Measurements of Hypoxic Tumor Volume: The blood oxygenation-based reversible transverse relaxation rate, R_2' , has been shown to be directly proportional to relative oxygen extraction fraction (rOEF), scaled by the relative cerebral blood volume (rCBV) (Hirsch et al., 2014; Toth et al., 2013). In the current study we will estimate R_2' using T_2 and T_2^* measurements obtained from the ME-SAGE component of the acquisition [$R_2' = (1/T_2^*) - (1/T_2)$]. If available, we will use rCBV measurements from dynamic susceptibility contrast (DSC) perfusion MRI to estimate $rOEF$ ($rOEF = R_2'/(c * rCBV)$, where c is a constant relating to the specific static magnetic field strength). Both mean R_2' and estimates of $rOEF$ within contrast enhancing and/or T2 hyperintense tumor regions will be used as exploratory measures of tumor hypoxia.

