Baseline tumor acidity and hypoxia will be defined both as continuous (e.g. mean $MTR_{asym} @ 3ppm$, mean R_2' , etc.) as well as categorical variables (i.e. acidic/hypoxic vs non-acidic/hypoxic) based on $>50\%$ of tumor having an acidic signature ($>3\% MTR_{asym} @ 3ppm$) or hypoxic signature ($R_2' > 5 s^{-1}$).

Descriptive statistics including the proportion of acidic/hypoxic and non-acidic/hypoxic lesions will be estimated with 95% confidence intervals. Fisher's exact test or other nonparametric analysis methods will be used to explore potential correlations between tumor acidity/hypoxia (imaging categorical variable) and tumor radiographic response.

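### The printed MTRasym formula (signal at +3 ppm minus signal at -3 ppm, over S0) has the opposite sign to the positive acidic cut-offs, if the amine offset is +3 ppm

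*Combined protocol and SAP*

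**What the plan says.** Section 9.5.4 names the acidity index: "the magnetization transfer ratio asymmetry at the amine proton off-resonance frequency ($MTR_{asym} @ 3ppm$) as a measure of tumor acidity". Section 2.4 gives the contrast mechanism, saying that exchange between amine and amide protons and bulk water "has been shown to be pH dependent using an imaging method called chemical exchange saturation transfer (CEST) imaging".

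Section 11.0, under the measurement of acidic tumour volume, gives the calculation. The wording is "calculating the difference in signal intensity between positive and negative offset frequencies divided by the signal intensity with no saturation", and the formula follows: "divided by the signal intensity with no saturation, $(S_{+3ppm} - S_{-3ppm})/S_0$, for each image voxel". The words alone do not fix a sign. The formula does.

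Section 11.0 then uses the index in three ways:

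- Volume: "Acidic tumor will be defined as having" an MTRasym at 3 ppm above 5%.
- Category: a tumour counts as acidic when more than 50% of it shows the signature ("of tumor having an acidic signature"), here set at above 3%. This category is compared with radiographic response by Fisher's exact test or another nonparametric method.
- Continuous: mean MTRasym is an exploratory measure of acidity.

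Both cut-offs are positive. Nowhere do the documents take an absolute value, print the terms in the other order, or state a sign convention for the offset.

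**The concern.** The index is built on saturation transfer. Saturating exchangeable protons at their own offset passes saturation to water and lowers the measured signal there. If the amine protons sit at +3 ppm, a stronger amine effect makes the +3 ppm signal smaller than the -3 ppm signal, and the printed difference is negative. A rule that calls tissue acidic above a positive value then points away from the tissue it is meant to find.

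Section 9.5.4 hypothesises that acidic or hypoxic tumours express high HIF2a and so are particularly amenable to treatment. The acidity half of that question depends on this classification. An analyst who programmed Section 11.0 as printed would get an acidic group that is almost empty or made up of the wrong tumours.

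**Working it through.** **Inputs from the documents**

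- Index as printed: (S at +3 ppm - S at -3 ppm) / S0 (Section 11.0).
- Acidic cut-offs: above +5% (volume) and above +3% in more than half the tumour (category), both in Section 11.0.
- Amine frequency: 3 ppm, sign not stated (Section 9.5.4).
- Patients expected to be analysable: at least 25 at full enrolment, or 16 if the trial stops early (Section 9.5.4).

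**Assumptions, not in the documents**

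- The amine frequency is the positive offset, +3 ppm.
- Saturation at an offset lowers the water signal measured there.
- Background signal m, as a share of S0, from 0.5 to 0.9; net amine loss a from 0 to 10% of S0. The protocol gives neither size.

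The plan states no figure to reproduce here, so the check evaluates the formula directly.

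**Step 1: amine effect only.** Put S(-3)/S0 = m and S(+3)/S0 = m - a.

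- As printed: (m - a) - m = -a.
- Terms reversed: m - (m - a) = +a.

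The background m cancels, so the results are the same at m = 0.5, 0.7 and 0.9:

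| Net amine effect a | As printed | Reversed | Reversed passes >3% | Reversed passes >5% |
|---|---|---|---|---|
| 0% | 0% | 0% | no | no |
| 2% | -2% | +2% | no | no |
| 4% | -4% | +4% | yes | no |
| 6% | -6% | +6% | yes | yes |
| 10% | -10% | +10% | yes | yes |

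The printed form passes neither cut-off in any row. As one example with illustrative signals, S0 = 1.00, S(-3) = 0.60 and S(+3) = 0.54: printed (0.54 - 0.60)/1.00 = -6%; reversed (0.60 - 0.54)/1.00 = +6%.

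**Step 2: allow a loss u on the negative side as well.** With S(-3)/S0 = m - u, the printed form gives u - a and the reversed form gives a - u.

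| Amine loss a | Loss at -3 ppm, u | As printed | Reversed |
|---|---|---|---|
| 3% | 2% | -1% | +1% |
| 3% | 10% | +7% | -7% |
| 6% | 2% | -4% | +4% |
| 6% | 12% | +6% | -6% |

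The printed index is positive only when the loss at -3 ppm exceeds the loss at +3 ppm. That is not an amine-driven signal.

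**Step 3: effect on classification.** For a positive cut-off c, a voxel is acidic as printed when u - a > c, and under the reversed order when a - u > c. These cannot both hold. Every voxel that passes under the reversed order is below -c as printed, so the two acidic sets do not overlap.

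**Step 4: effect on the test.** If no tumour reaches the acidic category, one row of the 2 x 2 table against response is empty and Fisher's exact test has nothing to compare. If a few reach it, they do so through loss at -3 ppm.

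**The case against.** The strongest reply is that the documents alone do not settle the sign. Section 9.5.4 says 3 ppm without a plus or minus, Section 2.4 says only that the contrast depends on pH, and the 5% cut-off rests on a cited study that is not available here. This stands in part. The conclusion needs the positive-offset reading and the general fact that saturation lowers signal. Nothing in the documents contradicts that reading, and a plan intending another convention would have to state it.

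A second reply is that sites do not calculate the index. Raw data go to one imaging laboratory (Section 9.5.4), and Section 11.0 has its imaging core process them by standard protocols, so the printed line may be a slip of notation. That is quite possible. It would mean that the plan does not describe the analysis performed, not that the printed rule is right. A sign error is also fully reversible from stored data.

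Three stronger inferences are tempting, and the documents do not support them:

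- A reader might infer that no acidic tumour can ever meet the cut-off. Step 2 shows that voxels with a larger loss at -3 ppm can exceed it, whatever their amine effect.
- A reader might infer that the trial would report acidic tumours as responding worse when they respond better. Section 11.0 names a response test only for the categorical variable, and that category would be empty or nearly so, which an analyst would notice. Mean MTRasym would have its sign reversed, but no specific test of it against response is laid down.
- A reader might infer that all the advanced imaging is affected. R2' and rOEF have their own formulas and are untouched. The listed objectives in Sections 1.0 and 11.0 name hypoxia, not acidity.

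**Conclusion.** The point holds as an inconsistency between the printed formula and the positive cut-offs, conditional on the amine offset being +3 ppm. Under that reading a net amine effect of a% of S0 scores -a%, whatever the background signal, so the rule classes true amine-effect voxels as non-acidic and can label as acidic only those with greater loss at -3 ppm.

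The sign result is algebraic and does not depend on the illustrative signal sizes. That the reversed mean would run against acidity also assumes that a larger amine effect means more acidic tissue, which is how Section 11.0 uses the index.

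The reach is small. It covers the acidity measures in about 16 to 25 patients, in imaging that the protocol calls strictly exploratory and bars from efficacy measurement. The primary endpoint, sample size and safety analyses do not use it. The difference between the 3% and 5% cut-offs is a separate issue: settling on either one does not correct the sign.

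**What to change.** In Section 11.0, define MTRasym at 3 ppm as (S at -3 ppm - S at +3 ppm) / S0. State beside it that the amine offset is +3 ppm relative to water and that higher values mean more acidic tissue. Ask the imaging core to confirm in writing that its pipeline uses this order and convention. If it uses another convention, print that one, so that formula, cut-off and code agree.

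The cost is one line of text and one confirmation. No scan, data collection or patient is affected, and any values already computed with the printed order can be corrected by changing their sign and reapplying the cut-off.

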Patient selection is a critical component of the therapeutic development of targeted agents. While hypoxia is central to the pathogenesis of GBM, biologic response to agents that target hypoxia pathways may vary based on the degree of hypoxia present, the reliance on hypoxic pathways, and other factors. As such, critical to the development of the proposed agent is the exploration of imaging and other methods to inform patient selection. While several modalities hold promise in imaging hypoxia, no clinically available gold standard currently exists. Two innovative hypoxia and pH-weighted MR-based imaging sequences have been recently developed by a collaborator through the ABTC ([name]/UCLA). These sequences and associated endpoints are an exploratory component of this study. The sequences will not be used to evaluate radiographic response or progression (i.e. PFS) and are not designed as companion or integral biomarkers in this study. Importantly, tumor hypoxia and acidity are hypothesized to be potential drivers of HIF2a expression and may not change as a result of HIF2a inhibition; however, pre-treatment levels of hypoxia and acidity may predict patients that respond from inhibition of HIF2a. The proposed advanced imaging will be performed at baseline to explore the degree of hypoxia present at treatment

initiation. The objective for this correlative imaging component of the study is to describe the hypoxia signature of these tumors at baseline and explore possible correlations with clinical outcomes.

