9.5.5.2 HIF Expression

Tumor tissue samples will be analyzed for HIF-2 α and HIF-1 α expression, and for the presence of other elements of the HIF pathway.

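### The named imaging-outcome analysis sets a two-category label against response, which will have few or no imaged responders; add a rank correlation of the continuous measures with tumour size change

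*Combined protocol and SAP*

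**What the plan says.** Section 11.0 (Hypoxia Imaging) states: "Baseline tumor acidity and hypoxia will be defined both as continuous", with mean MTRasym at 3 ppm and mean R2' as examples, and also as a categorical label. One sentence then links imaging to outcome: Fisher's exact test, or another nonparametric method, is to "explore potential correlations between tumor acidity/hypoxia (imaging categorical variable) and tumor radiographic response". No outcome analysis is attached to the continuous measures, and none relates imaging to progression-free or overall survival.

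The aim in Section 2.4 is wider: to describe the hypoxia signature and "explore possible correlations with clinical outcomes". Section 9.5.4 anticipates "at least 25 patients (if the study proceeds to full enrollment) or 16 patients" (the latter after early stopping) as analysable, and calls this imaging exploratory and optional.

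Two further statements matter here:

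- Section 11.0 gives two acidity cutoffs for MTRasym at 3 ppm: above 5% where acidic tumour volume is measured, and above 3% where the categorical label is defined.
- Section 9.5.4 hypothesises that "patients with acidic or hypoxic tumors will likely express high levels of HIF2a", and Section 9.5.5.2 says "Tumor tissue samples will be analyzed for HIF-2 α and HIF-1 α expression". Section 11.0 does not relate the two.

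**The concern.** Section 2.4 presents the imaging as a way to inform patient selection for a HIF2a inhibitor. The named analysis reduces the imaging measure to two categories and the outcome to response yes or no. Responders are the scarcest data in this trial: the design stops at 0 or 1 in 24 and declares success at 5 in 35, and only some of them will have been imaged. Meanwhile the continuous imaging measures and the bidimensional tumour measurements required by Section 8.1 are collected and not related to each other. At stake is whether the imaging can say anything about outcome, above all if the trial stops early.

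**Working it through.** **Inputs.** Stage 1: 24 patients, stop at 0 or 1 responder. Final: 35 patients, reject the null at 5 responders (read as at least 5). Response rates 5% and 20% (all Section 11.0). Imaged patients: 16 or 25 (Section 9.5.4).

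**The plan's own figures.** Under the null, P(0 of 24) = 0.95^24 = 0.292 and P(1 of 24) = 24 × 0.05 × 0.95^23 = 0.369. Their sum is 0.661, as stated. At 20% the stop probability is 0.033, as stated. Overall power is 0.852 and the actual false positive rate is 0.028, within the stated 85% and 5%.

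**Stage 1 stop, 16 imaged.**
- With one imaged responder, the smallest Fisher p is 1/N = 1/16 = 0.0625, and only if that patient is alone in a category. At an 8/8 split p = 1.0.
- With no imaged responder there is nothing to test. If imaging is independent of response, P(exactly one responder, and imaged) = 0.369 × 16/24 = 0.25 under the null. The remaining 0.661 − 0.25 = 0.41 has no imaged responder.
- The floor of 1/N is 0.050 at 20 imaged and 0.048 at 21. From 21 imaged, a one-patient category could cross 0.05, which has no practical value.
- Moving only the imaging side to a continuous scale does not help. A rank test of the measure against one responder in 16 has a minimum two-sided p of 2/16 = 0.125. The outcome side has to change too.

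**Full size, 25 imaged, 5 responders in 35.**
- Expected imaged responders: 5 × 25/35 = 3.6.
- Hypergeometric: P(4) = C(25,4) × 10 / C(35,5) = 126,500/324,632 = 0.390; P(5) = 53,130/324,632 = 0.164. So P(3 or fewer) = 1 − 0.553 = 0.45.
- Best p at a 12/13 split, all responders in the group of 12: 3 responders, C(12,3)/C(25,3) = 220/2,300 = 0.096; 4 responders, C(12,4)/C(25,4) = 495/12,650 = 0.039; 5 responders, 0.015.
- If all 4 fall in the group of 13, p = (715 + 495)/12,650 = 0.096.
- Exact Fisher power at 12/13, for assumed response rates by label: 30% v 10%, 18%; 35% v 5%, 42%; 40% v 0%, 78%.

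**Alternative.** Spearman correlation of the continuous measure with percent change in tumour size was compared by simulation with Fisher on a median-split label and response. The model is bivariate normal, n=25, with 20% responding. The latent correlation is an assumption, since the documents give none.

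| Latent correlation | Fisher | Spearman | Spearman, 20% ranked worst at random |
|---|---|---|---|
| 0.3 | about 9% | about 27% | about 15% |
| 0.5 | about 22% | about 69% | about 32% |

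With no association, Spearman rejects in about 5% of simulated trials. At n=16 with 5% responding, Spearman has about 18% (correlation 0.3) to 47% (0.5) with complete scans; Fisher has essentially none.

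**The case against.** The strongest reply is that this is a descriptive, optional correlative. Section 1.0 lists only description of baseline hypoxia, and the proportions with 95% confidence intervals in Section 11.0 deliver that whatever the Fisher result. No alpha or power is set, so failing to reach 0.05 breaches nothing. A drug with 0 or 1 responder in 24 leaves little response to predict under any test. All of this stands, and it limits the weight of the point. It does not explain why the continuous measures have no outcome analysis, given the aim in Section 2.4.

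A reader might infer more than the documents support:

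- *That Fisher is the only test allowed.* The text also permits other nonparametric methods, though still for the categorical label against response.
- *That most of the information is discarded.* A median split of a normal measure keeps about 64%. The loss passes half only near an 80/20 split, and the documents give no expected split. Counting a 20% response cut as well would leave about 0.64 × 0.49 = 31%, but that rests on a bivariate normal model.
- *That 0.661 is the chance of one imaged responder.* It is the chance of 0 or 1 responder in 24.
- *That the imaging and response reads are unmasked.* The UCLA core has a part in both, but response is first assessed locally (Section 8.4) and nothing says the same readers do both.
- *That correlating imaging with HIF-2α would test the Section 9.5.4 hypothesis.* The tissue is archival and may date from the initial resection (Section 9.5.5), before the radiation and temozolomide that preceded the imaging.

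The alternative has limits too. Only scans of locally assessed responders are centrally reviewed (Sections 8.2 and 8.4), so percent change in non-responders rests on local reads. Its advantage over Fisher also narrows sharply if many patients are ranked worst for unrelated reasons.

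**Conclusion.** The point holds as a low-cost improvement to an exploratory analysis; no primary or secondary conclusion depends on it. With 16 imaged after a stage 1 stop, the named Fisher test has a floor of p = 0.0625 or cannot be run, and that stop has probability 0.661 under the null. With 25 imaged and 5 responders in 35, there is a 45% chance of 3 or fewer imaged responders, where a near-even split cannot do better than 0.096. These results are exact, given the anticipated imaged numbers and, for the 45%, imaging independent of response. The use of 0.05 is a yardstick, not a criterion of the plan.

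The gain from the rank correlation depends on an association the documents do not quantify: at n=25, about 27% to 69% against 9% to 22%, or about 15% to 32% under unfavourable missingness. Part of it comes from using a different outcome, not only a different test.

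**What to change.** In Section 11.0 (Hypoxia Imaging):

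1. Add as the main exploratory imaging-outcome analysis the Spearman correlation, with 95% confidence interval, of mean MTRasym at 3 ppm and of mean R2' with best percent change from baseline in the sum of products of diameters. Keep Fisher's test as secondary.
2. Rank a patient without a post-baseline scan as worst only when the reason is death or deterioration, which Section 8.1 already counts as progression. State in advance how other patients without a scan are handled, and report a sensitivity analysis that excludes them.
3. Reconcile the two acidity cutoffs (above 5% and above 3%), and fix the categorical label before response data are seen.
4. Optionally, report the correlation of the imaging measures with HIF-2α expression, giving the date of the tissue and reading it with caution.

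The cost is SAP wording and a few lines of code, with no new data. The downsides are more exploratory estimates without multiplicity control, and reliance on local tumour measurements in non-responders.
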